3. STUDY DESIGN

A placebo controlled, double blind, randomized clinical pilot study of mild to severe asthmatics treated in a 1:1 ratio with oral ginger 1 gm twice per day or matching placebo.

18 subjects will be assigned to each of two arms (ginger vs. placebo). This is defined by a power analysis requiring 16 subjects per arm and a 10% projected attrition rate. Subjects will be evaluated 5 times during the study, at screening, baseline methacholine testing, at the initial randomization visit and at days 28 and 56 while taking ginger or placebo.

The primary outcomes will be the improved tolerance to the bronchoconstrictive effect (reduced airway hyperresponsiveness) of inhaled methacholine (methacholine PD₂₀) or a reduction in exhaled nitric oxide. Secondary outcomes will include an improvement in baseline FEV1 of 100ml, a reduction in eosinophilia or a reduction in asthma associated serum cytokines. An additional secondary outcome will be defining the pharmacokinetic profile of active components of ginger in adult asthmatics.

Grant phase	Spec. Aim	Primary outcome	Clinically Significant Change [ref]	Means ± S.D; examples from literature [ref] (units)	Sample Size \group	# of groups	Sample size required	Sample Size required with 10% attrition
R61	1	Mch PD ₂₀ doubling dose	Increase of 0.7 in Mch doubling dose ¹²	1.07 ± 0.6 1.73 ± 0.6 (Mch doubling dose) ¹²	14	2 2g/day ginger placebo	28	32
	2	Exhaled nitric oxide	20% decr for >50 ppb or decr of 10ppb for <50ppb ¹³	74 ± 37 37 ± 34 (ppb) ¹⁴	16	2 2g/day ginger placebo	32	36 for aims 1&2

Outpatient; The John Edsall-John Wood Asthma Center at the Columbia University Medical Center

Individual enrollment: 78 +/- 7 days. Enrollment period 12 months, Entire trial (first subject screened to last patient completed): 20 months.

Screening/Run-In Period

Adults 18 and older, with physician diagnosed mild to severe persistent asthma will be screened. After reviewing and signing informed consent, subjects that fulfill inclusion and exclusion criteria will be invited to participate.

Day 0/Visit 1: Screening Visit: review of medical history, recording of medication use, physical exam by study MD or NP, scoring on ACT and basic spirometry before and after bronchodilator. Subjects will then be asked to continue their usual asthma medications for the 14-21 day run-in period.

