Post-Bronchodilator Spirometry: Will be performed 15 mins after inhalation of 4 puffs of a short acting Bronchodilator.

Methacholine Provocation: A methacholine challenge test is a medical test used to assist in the diagnosis of asthma. The patient breathes in nebulized methacholine at gradually increasing doubling doses, starting with diluent only. Methacholine provokes bronchoconstriction, or narrowing of the airways via M3 receptors. The degree of narrowing can then be quantified by spirometry which is performed after inhalation of each dose. Once the FEV1 drops by 20% or more from baseline diluent spirometry, the test is halted.

Methacholine Recovery Challenge Albuterol will be administered by inhalation (4 puffs) at the end of the methacholine provocation test to return the patients FEV1 back to baseline:

GI side effect checklist: Patients will be asked about the frequency and severity of GI symptoms including eructation, heartburn, nausea, bloating or indigestion at Visits 3,4 and 5.

Measured Exhaled Nitric Oxide (FeNO): FeNO is widely used as a global measure of lung inflammation. Exhaled breath will be collected from forced expirations using disposable mouthpieces for the online exhaled NO (Circassia) procedure described in the American Thoracic Society (ATS) guidelines. FeNO levels will be measured at Visits 3,4 and 5.

Blood Draw for Cytokines, eosinophilia, biomarkers: Peripheral venous blood will be collected at Visit 3, 4 and 5 for the measurement eosinophils and cytokines and biomarkers. 8 subjects will also have blood collected for pharmacokinetic studies. Eosinophils counts will be measured in the Center for Advanced Laboratory Medicine (CALM) lab in the Department of Pathology at Columbia University located at [name]. Multiplex cytokine analyses will be performed in the laboratory of [name], Department of Anesthesiology, [name].

Enrollment/Randomization: Randomization to either ginger capsules or placebo will be done using a randomization algorithm within REDCap in a blinded fashion (group A or B).

Pre-Dose blood draw for PK subjects: Study drug should be withheld the day of the study visit for the PK subgroup. Study drug will be administered in the clinic after the pre-dose PK blood draw

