6.2.1 Screening Evaluation

Adults 18 and older, with physician diagnosed mild to severe persistent asthma will be screened. After reviewing and signing informed consent, subjects that fulfill inclusion and exclusion criteria will be invited to participate.

Consenting Procedure

Single informed consent describing screening and study procedures.

The study PI ([name]) or the research study coordinator ([name]) will conduct the consent process.

[name] is a professor of medicine and pulmonologist and director of the John Edsall-John Wood Asthma Center at Columbia University Medical Center. [name], B.S. has over 3 years of experience as a clinical research coordinator and has experience consenting and studying pulmonary

patients during clinical studies in the John Edsall-John Wood Asthma Center.

Any changes in the consent form will only occur after approval from the institutional IRB and the NCCIH.

Documentation of the consent process and consent forms will be retained in a research study binder.

Screening

Visit 1: Screening Visit

Sequence of events:

- Identify patients that are adults 18 and older with physician-diagnosed mild to severe persistent asthma
- Sign informed consent
- Fulfill inclusion and exclusion criteria
- Review of medical history
- Record Demographics
- Recording of medication use
- Physical exam including vital signs by study MD or NP
- Urine pregnancy test for women of child bearing age
- Scoring on ACT ≤ 19
- Scoring on basic spirometry before and after bronchodilator

Required to be eligible:

- Patients that are adults 18 and older with physician-diagnosed mild to severe persistent asthma
- Signing informed consent
- Fulfill inclusion and exclusion criteria
- Using inhaled corticosteroids with or without inhaled long acting beta agonists or anti-muscarinics.
- Scoring on ACT ≤ 19
- Negative urine pregnancy test for women of child bearing age

Screening must be completed 14-21 days prior to visit 2 during which the ACT score will be confirmed to be ≤ 19 , and the baseline FEV1 is $\geq 60\%$ of predicted (or 1.5L); Baseline methacholine PD20 will be determined at V2 as a subsequent eligibility criterion.

Visit 2; Day 14 to 21:

- Administer ACT. If ACT remains ≤ 19 , proceed . If ACT > 19 consistent with good asthma control, terminate from study.
- Confirm medication washouts (reschedule if not met).
- Spirometry

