- methacholine bronchoprovocation testing if FEV1 is $\geq 60\%$ or 1.5L (reschedule or terminate if $< 60\%$ or 1.5L) to assess baseline methacholine PD20.
- Administer BD for Methacholine Recovery Challenge

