9.5.1 Primary Outcome

The primary outcomes are a clinically significant change in tolerance to inhaled methacholine (PD₂₀) or a clinically significant change in exhaled nitric oxide. These outcomes will be measured at visit 3 (baseline) and visits 4 and 5 (days 28 and 56 of the oral ginger or placebo consumption).

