9.6 Data Analyses

We will compare the change in log-transformed methacholine reactivity (PD₂₀) in the ginger versus the placebo group using two-sample t-test. We will compare patients' initial PD₂₀ (day 0) to their subsequent PD₂₀ at days 28, 56 using paired t-test. It is possible that the PD₂₀ measurements on days 0, 28 and 56 could be influenced by the consumption of oral ginger 1 hour prior so we will also compare the PD₂₀ at

day 0 to those at 28 and 56. An acute benefit in methacholine tolerance will be reflected in a significant improvement between PD₂₀'s at days 0, 28 and 56 while a chronic improvement will be reflected in improved PD₂₀'s at days 28 and 56 compared to day 0.

Patients with asthma have remarkably consistent fractional exhaled nitric oxide (FeNO) levels when measured over time with mild-moderate asthmatics having FeNO values of approximately 40 ± 10 ppb.²² We will consider a 25% change in FeNO as biologically significant²³ comparing each patient's initial FeNO to their subsequent FeNO at days 28, 56 using paired t-test.

Data from prior studies does not support the existence of significant differences in the intervention effect between subgroups and thus subgroup analysis will not be performed.

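### Section 9.6 cannot separate an acute from a chronic PD20 benefit: both are read from the same three challenges, none scheduled 1 hour after a dose, and Sections 9.1 and 9.5.1 name the wrong PD20 baseline visit

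*Combined protocol and SAP*

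**What the plan says.** Section 9.6 lists a two-sample t-test between arms on the change in log PD20, then paired t-tests of day 0 against days 28 and 56. It adds that PD20 "measurements on days 0, 28 and 56 could be influenced by the consumption of oral ginger 1 hour prior", and for that reason plans a further comparison of day 0 with days 28 and 56. The interpretation follows: "An acute benefit in methacholine tolerance will be reflected in a significant improvement between" the values at days 0, 28 and 56, "while a chronic improvement will be reflected in improved" values at days 28 and 56 relative to day 0.

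On timing, Section 6.1 marks the methacholine challenge at Visits 2, 4 and 5. Section 3 lists the evaluations as "at screening, baseline methacholine testing, at the initial randomization visit and at days 28 and 56", so the baseline challenge and the randomization visit are separate occasions. Section 6.2.1 states "Baseline methacholine PD20 will be determined at V2 as a subsequent eligibility criterion", and its Visit 2 list includes a challenge "to assess baseline methacholine PD20". The first dose is given at Visit 3 (Section 6.2.4).

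On the baseline label, Section 9.5.1 says of both primary outcomes, "These outcomes will be measured at visit 3 (baseline) and visits 4 and 5", and Section 9.1 has the same sentence. For exhaled nitric oxide this agrees with Section 6.2: "FeNO levels will be measured at Visits 3,4 and 5".

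**The concern.** The plan attaches two mechanistic conclusions to one set of contrasts. If PD20 rises in the ginger arm at both days 28 and 56, the acute and the chronic definitions are both met, whatever the mechanism. A report that follows Section 9.6 could then claim an acute gain in methacholine tolerance that no scheduled challenge measures.

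The paired tests have a second weakness. A within-arm rise can come from a change that both arms share, and only the between-arm test separates that from an effect of ginger.

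The baseline label is a smaller matter. A reader of Section 9.5.1 alone would look for a Visit 3 PD20 that does not exist. The name day 0 in Section 9.6 does not help, because the précis and Section 3 use Day 0 for the screening visit, where no challenge is done.

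**Working it through.** **1. Challenges set against dosing**

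| Visit | Challenge (6.1) | Study drug before the challenge |
|---|---|---|
| 2 | yes | none; the first dose comes 1 to 2 days later, at Visit 3 |
| 3 | no | first dose; spirometry 1 hour later (6.2) |
| 4 | yes | morning dose withheld (précis, Section 3); challenge listed before dosing (6.2.4) |
| 5 | yes | as for Visit 4 (challenge listed before dosing in 6.2.4 and 6.2.5) |

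Challenges: 3. Challenges scheduled 1 hour after a dose: 0.

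**2. Can the two effects be estimated?** Write the six arm-by-visit means of log PD20 with five parameters: a common baseline, a shared shift at day 28, a shared shift at day 56, an acute ginger effect (dose about 1 hour earlier) and a chronic ginger effect (repeated dosing).

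- Documented schedule: the acute column is zero everywhere. Rank 4 of 5, so the acute effect is not estimable.
- Doses taken 1 hour before Visits 4 and 5 only: the acute and chronic columns are identical. Rank 4 of 5, so the two are fully confounded.
- Doses taken 1 hour before all three challenges: rank 5 of 5, but only through the between-arm comparison. No such challenge is scheduled at baseline.

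The paired tests in 9.6 use the ginger arm alone, with three parameters (baseline, acute, chronic). Their rank is 2 of 3 in all three cases. The contrast of day 56 with day 28 adds nothing independent, because it is the difference of the two contrasts already taken.

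**3. The plan's own figure.** Section 9.2 gives 14 per arm for PD20. With SD 0.6, 80% power and two-sided 0.05 (sidedness is not stated, so this is assumed), a difference of 0.7 needs 12 per arm by the normal formula and 13 by t. The Section 3 table means differ by 1.73 − 1.07 = 0.66, which needs 13 by the normal formula; by t, 14 per arm gives 80.0% power. The stated 14 is reproduced, and nothing in this point changes it.

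**4. How often would a purely chronic effect meet the acute wording?** Take a gain of 0.66 or 0.7 doubling doses in the ginger arm, equal at days 28 and 56, with no acute component. Assume that placebo does not change, that the 0.6 of Section 9.2 is the SD of each change, n = 16, and a correlation of 0.3, 0.5 or 0.8 between the two changes. For a single paired test the noncentrality is gain ÷ (SD/√16). That is 0.66/0.15 = 4.4 or 0.7/0.15 = 4.67, giving power of 98.4% or 99.2%. Both tests significant in the improving direction (200,000 simulations per cell):

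| Gain | SD 0.6 | SD 1.0 |
|---|---|---|
| 0.66 | 0.969 / 0.970 / 0.974 | 0.519 / 0.546 / 0.600 |
| 0.70 | 0.984 / 0.984 / 0.986 | 0.585 / 0.610 / 0.660 |

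If the acute wording is read as also requiring a significant rise from day 28 to day 56, the probability is 0.022 to 0.024 (SD 0.6) or 0.006 to 0.012 (SD 1.0).

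**5. Baseline adjustment of the between-arm test.** Unadjusted, 16 per arm and SD of change 0.6 (30 df): power 0.853 for 0.66 and 0.891 for 0.7. Adjusting for Visit 2 log PD20 multiplies the variance by (1 + ρ)/2, assuming equal variances at the two visits, with 29 df. For ρ = 0.5 / 0.7 / 0.8 / 0.9:

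- 0.66: 0.935 / 0.903 / 0.887 / 0.870
- 0.70: 0.957 / 0.933 / 0.919 / 0.905

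**The case against.** The best case against this point concerns its weight. An acute PD20 benefit is not among the objectives or outcomes, the between-arm test comes first in Section 9.6, and no primary or secondary conclusion changes. That stands, and it limits the point to a supplementary interpretation.

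The 97 to 99% is the power of two paired tests when a real effect exists, so it illustrates the overlap and does not prove it. It turns a between-group difference into a within-arm gain by holding placebo still, and it takes 0.6 as an SD of change, which Section 9.2 does not say. On the stricter reading the figure falls to about 1 to 2%. All of this is fair. The firm results are the count of 0 in 3 and the rank argument. The stricter reading does not rescue the plan either, because a rise from day 28 to day 56 shows further gain on treatment, not an acute effect.

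A further objection is that Sections 5.1 and 6.2 state withholding for the pharmacokinetic subgroup only, so other subjects might take a dose before the Visit 4 and 5 challenges. The text is indeed inconsistent here. But such doses would be at uncontrolled times, and the baseline challenge would still precede any study drug, so acute and chronic effects would remain inseparable.

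Finally, the Visit 2 baseline is clear from Sections 3, 6.1 and 6.2.1, so the label is a correction and the data are not in doubt. Baseline adjustment is unrelated to the defect: unadjusted power of 85 to 89% already exceeds the 80% target. It is offered only as an improvement that costs nothing.

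**Conclusion.** The point holds. Under the documented schedule an acute effect on PD20 is not estimable, and the definitions in Section 9.6 would let a purely chronic gain be reported as acute. This rests on the schedule alone. The 97 to 99% (52 to 66% at SD 1.0) depends on the assumptions of unchanged placebo, equal gains at the two visits and 16 subjects, and on the plain reading of the acute definition. The PD20 baseline label in Sections 9.1 and 9.5.1 is wrong for PD20 and right for exhaled nitric oxide. The between-arm PD20 test and the sample size stand. The text should be corrected, but the damage is confined to a secondary interpretation of a primary outcome.

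**What to change.** 1. In Section 9.6, delete the acute PD20 comparison and its interpretation. Make the within-arm paired PD20 tests descriptive and base PD20 conclusions on the between-arm comparison.
2. In Sections 9.1, 9.5.1 and 9.6, state that the PD20 baseline is Visit 2 and the exhaled nitric oxide baseline is Visit 3, and replace day 0 in 9.6 with the visit number.
3. If an acute effect is of interest, compare between arms the Visit 3 change in FEV1 from pre-dose to 1 hour post-dose. Section 6.2 already collects it to look for acute bronchodilation. Label it exploratory, and as bronchodilation, not methacholine tolerance.
4. As a separate improvement, adjust the between-arm PD20 comparison for Visit 2 log PD20. Power would rise from 85% to 87–94% for a difference of 0.66, and from 89% to 91–96% for 0.7, for assumed correlations of 0.9 down to 0.5.

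The dosing passages also need reconciling. The précis and Section 3 state withholding of the morning dose for all subjects, but Sections 5.1 and 6.2 state it for the pharmacokinetic subgroup. Visit 5 dosing is limited to that subgroup in 6.2.4 but not in 6.1 or 6.2.5. No rule is proposed here.

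The cost is protocol and SAP wording only. Items 3 and 4 use data already collected, with no new visits, procedures or participants.

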6. STUDY PROCEDURES

6.1 Schedule of Evaluations

Assessment	Screening: Visit 1 (Day 1)	Baseline, Enrollment Visit 2 (Day 14-21)	Study & Randomization Visit 3 (Day 15-22)	Study Visit Visit 4 (Day 43-50)	Study Visit Visit 5 (Day 71-78)
Informed Consent Form	X				
Demographics	X				
Administer Asthma Control Test (ACT)	X	X	X	X	X
Administer QOL questionnaire			X	X	X
Administer 2 week recall questionnaire			X	X	X
Confirm Medication Washouts	X	X	X	X	X
Medical History	X		X		
General Physical Examination	X		X	X	X
Urine pregnancy test for women of childbearing age	X		X	X	X
Inclusion/Exclusion Criteria	X		X		
Vital Signs	X		X	X	X
Spirometry	X	X	X	X	X
Post-Bronchodilator Spirometry	X				
Methacholine Bronchoprovocation		X		X	X
Administer bronchodilator	X	X		X	X
Methacholine Recovery challenge		X		X	X
GI side effects checklist			X	X	X
Measure exhaled nitric oxide			X	X	X
Blood draw for cytokines, eosinophilia, biomarkers			X	X	X
Enrollment/Randomization			X		
Pre-dose blood draw for PK subjects			X	X	X
Administer dose of study drug			X	X	X
Post dose spirometry (1hr)			X		
PK blood draws for selected subjects			X	X	X
Dispense drug			X	X	
IP Accountability				X	X
Concomitant Medications	X	X	X	X	X
Adverse Events	X	X	X	X	X

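### Section 9.6 reads an acute PD20 benefit from methacholine tests that no scheduled dose precedes by one hour, and Sections 9.1 and 9.5.1 put the PD20 baseline at a visit with no methacholine test

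*Combined protocol and SAP*

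**What the plan says.** Section 9.6 compares change in log PD20 between ginger and placebo by a two-sample t-test, and compares each patient's initial (day 0) PD20 with days 28 and 56 by paired t-test. It adds that the three PD20 values "could be influenced by the consumption of oral ginger 1 hour prior" and, for that reason, proposes to compare day 0 with days 28 and 56. It then gives two reading rules. The first is that "An acute benefit in methacholine tolerance will be reflected in a significant improvement between" the values at days 0, 28 and 56. The second follows in the same sentence: "while a chronic improvement will be reflected in improved" values at days 28 and 56 compared with day 0.

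On the baseline visit, Sections 9.1 and 9.5.1 say of the primary outcomes, PD20 and exhaled nitric oxide together: "These outcomes will be measured at visit 3 (baseline) and visits 4 and 5". Section 6.2.1 says otherwise for PD20: "Baseline methacholine PD20 will be determined at V2 as a subsequent eligibility criterion". Its Visit 2 list includes the challenge "to assess baseline methacholine PD20". In the Section 6.1 schedule, the row "Methacholine Bronchoprovocation" is marked at Visits 2, 4 and 5 and is empty at Visits 1 and 3.

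On dosing, Section 3 puts the first capsule at Visit 3, one to two days after Visit 2, with spirometry repeated an hour later. The Précis and Section 3 ask all subjects to skip the morning dose on the day of Visits 4 and 5. Section 5.1 and the pre-dose blood draw entry in Section 6.2 state a hold for pharmacokinetic (PK) subjects only.

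**The concern.** PD20 is one of two primary outcomes, and Section 9.6 fixes in advance how its changes will be interpreted. To show an acute effect, PD20 must be measured shortly after a dose and compared with a measurement not so affected. The schedule contains no such pair. An analyst following Section 9.6 could report an acute effect of ginger on methacholine tolerance that the tests cannot show, or describe one day 0 to day 28 or 56 change as both acute and chronic.

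The baseline statement adds a smaller problem. Read literally, Sections 9.1 and 9.5.1 send the analyst to Visit 3 for a PD20 value that is not collected there.

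**Working it through.** **1. Tests and doses, side by side**

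| Methacholine test | Source for the test | Study dose specified one hour before? | Source for dosing |
|---|---|---|---|
| Visit 2 (baseline) | Sections 6.1, 6.2.1 | No: first capsule is at Visit 3, 1-2 days later | Section 3 |
| Visit 4 (day 28 of drug) | Sections 6.1, 6.2.4 | No: morning dose withheld | Précis, Section 3 |
| Visit 5 (day 56 of drug) | Sections 6.1, 6.2.4, 6.2.5 | No: morning dose withheld | Précis, Section 3 |

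Count: 0 of 3. The only measurement scheduled one hour after a dose is spirometry at Visit 3.

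**2. What the within-subject contrasts contain**

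Assume that effects add on the log PD20 scale. Let m be the pre-treatment level, A the effect of a dose taken one hour before the test, and C28 and C56 the changes accrued by days 28 and 56. Let d be 1 if a dose preceded the test by an hour and 0 if not. Then:

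- Y0 = m + A·d0
- Y28 = m + A·d28 + C28
- Y56 = m + A·d56 + C56

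The three pairwise contrasts are:

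- Y28 − Y0 = C28 + A(d28 − d0)
- Y56 − Y0 = C56 + A(d56 − d0)
- Y56 − Y28 = C56 − C28 + A(d56 − d28)

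| Case | (d0, d28, d56) | Y28 − Y0 | Y56 − Y0 | Y56 − Y28 |
|---|---|---|---|---|
| Schedule as written | (0, 0, 0) | C28 | C56 | C56 − C28 |
| Section 9.6 premise: dose before all three | (1, 1, 1) | C28 | C56 | C56 − C28 |
| Hold missed at both follow-up tests | (0, 1, 1) | C28 + A | C56 + A | C56 − C28 |

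In the first two cases A appears in 0 of 3 contrasts. In the third it appears in 2 of 3, each time added to a chronic term. The extra day 0 versus 28 and 56 comparison that Section 9.6 proposes as a response to recent dosing is the paired comparison it has already listed, so it brings no new information.

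**3. The baseline visit**

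Sections 9.1 and 9.5.1 say Visit 3 for both primary outcomes. Section 6.1 marks exhaled nitric oxide at Visit 3, so that half is right. It marks no methacholine test there, and Section 6.2.1 takes the baseline PD20 at Visit 2. The error is confined to PD20.

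**4. The sample size**

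The stated 14 per arm for PD20 can be reproduced. The example means in the Section 3 table differ by 1.73 − 1.07 = 0.66; with SD 0.6, two-sided 0.05 and 80% power, the t-based calculation gives 14.0. Neither the acute reading nor the baseline label is an input, so the figure does not move.

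**The case against.** The strongest reply is that little depends on this. Only one pre-treatment PD20 exists, Section 9.6 calls it the patient's initial value, and Section 3 lists baseline methacholine testing separately from the randomisation visit. An analyst has no other value to use. The two-sample comparison of change in log PD20 can be run as planned. All of this stands, and it limits the severity.

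Several stronger readings are tempting but are not supported:

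- **That an acute effect could not be estimated under any analysis, because the unknowns outnumber the tests.** Counting unknowns does not prove this. If a dose really preceded all three tests, the ginger minus placebo difference at day 0 would estimate A, since randomisation balances m in expectation. The narrower statement holds: A is absent from the within-subject contrasts, and the actual day 0 test precedes any study drug.
- **That the visit lists prove dosing follows the challenge.** The Visit 4 and 5 lists are headed as procedures, not as a sequence, unlike the Visit 1 list. The finding rests on the withheld dose.
- **That day 0 in Section 9.6 means screening.** Section 3 does use that label ("Day 0/Visit 1: Screening Visit: review of medical history, recording of medication use"), but days 0, 28 and 56 in Section 9.6 are more naturally treatment-time labels.
- **That non-PK subjects are told to dose before testing.** Section 5.1 and the Section 6.2 blood draw entry limit the hold to PK subjects, which conflicts in scope with the Précis and Section 3. A non-PK subject following the narrower text might dose at home, but no text sets that dose one hour before methacholine.

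It is also fair to say that one-hour post-dose FEV1 is not a listed primary or secondary outcome, and that it measures bronchodilation, not methacholine tolerance. It can support only an exploratory analysis.

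**Conclusion.** The point holds in two parts. First, the acute PD20 inference in Section 9.6 has no basis in the schedule: 0 of 3 methacholine tests have a protocol-specified dose one hour earlier, and the acute and chronic rules use the same day 0 versus 28 and 56 comparisons. Second, Sections 9.1 and 9.5.1 name the wrong baseline visit for PD20.

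A reader might infer that the primary PD20 analysis is biased or underpowered as a result. The documents do not support that. The randomised comparison of change in log PD20 is unaffected once Visit 2 is used as baseline, and no bias or sample-size effect is claimed.

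The conclusion assumes additive effects on the log scale and that the all-subject hold in the Précis and Section 3 is the intended rule. If the hold were missed at both follow-up visits, the within-subject changes would mix acute and chronic effects; they would still not separate them. Severity is minor to should-fix, limited to the acute inference and the baseline visit.

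**What to change.** 1. In Section 9.6, delete the premise of a dose one hour earlier and the acute PD20 inference. State that PD20 at days 28 and 56 is a pre-dose measure compared with the Visit 2 baseline.
2. In Sections 9.1 and 9.5.1, name Visit 2 as the PD20 baseline and keep Visit 3 for exhaled nitric oxide.
3. Assess any acute effect only as acute bronchodilation. Add one line to Section 9.6 comparing the Visit 3 change in FEV1, pre-dose to one hour post-dose, between ginger and placebo, labelled exploratory. Section 6.2 already collects this spirometry for that purpose, and Section 9.6 gives no analysis of it.
4. Change Section 5.1 and the pre-dose blood draw entry in Section 6.2 to match the all-subject hold in the Précis and Section 3. Record the time of the last study dose at Visits 4 and 5, and do not make a missed hold a ground for removal.

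Study drug should not be added to the washout table in Section 4.1. Section 6.2 reschedules visits when washouts fail, and Section 10.3.4 removes subjects who miss visit windows, so one capsule could cost a subject in a trial of 18 per arm.

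The cost is protocol wording, one recorded time at each of two visits, and one exploratory comparison. No visits, tests or patients are added.
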